Study Design

NCT numer: *pending*

Title: Assessment of Vascular Complications in Patients Undergoing Peripheral Revascularization: The Impact of SGLT-2 Inhibitors

Type: Retrospective, observational study

1. **Study Objective:** To assess the impact of SGLT2 inhibitors on vascular complications in patients undergoing peripheral revascularization.

Specific Objective: To evaluate the occurrence of 3-point MACE (Major Adverse Cardiac Events) or MALE (Major Adverse Limb Events) after vascular surgery procedures (both open and minimally invasive), performed electively or urgently, in patients previously treated with SGLT2 inhibitors.

Follow-up period: ONE YEAR: assessment at 30 days, 3 months, and 12 months post-procedure.

Definition of MACE:

Myocardial infarction (MI) not resulting in death

Stroke affecting the central nervous system (CNS) not resulting in death

Cardiovascular death

**Definition of MALE:*

Untreated loss or deterioration of patency in a previously revascularized vessel (decline in ABPI)

Repeat intervention in the revascularized segment due to loss of patency

Amputation (above or below the knee) of the revascularized limb

2. **Primary Outcome Measures:** MALE and MACE

3. **Secondary Outcome Measures:** Individual components of MALE and MACE

4. **Additional Secondary Outcome Measures:**

Surgical complications such as surgical site infection (SSI) or major bleeding

Acute kidney injury

Need for reintervention (readmission and procedure in the same segment)

Foot necrosis

“Minor amputation” (defined as amputation within the foot)

Hospitalization due to heart failure

5. Inclusion and Exclusion Criteria

Inclusion Criteria:

Surgical procedure on peripheral vessels due to acute or chronic ischemia

Use of SGLT2 inhibitors (reason for initiation is irrelevant: CKD – chronic kidney disease / cardiovascular indications / diabetes) - Condition required only for the drug-exposed group.

Ability to follow up the patient for at least 30 days up to 1 year after the vascular procedure

Exclusion Criteria:

Vascular injury as the reason for the procedure

Amputation for reasons other than ischemia (e.g., tumor, neuropathy, trauma without concomitant ischemia)

Planned revascularization procedure not involving lower limbs (e.g., coronary or carotid vessels)

Planned amputation due to ischemia, partial, in the area of the operated limb

Planned other major surgical procedure with high cardiovascular risk

6. Collected Parameters (at admission to the vascular surgery ward):

Laboratory tests:

Complete blood count

Blood creatinine with eGFR

Urinalysis

Full lipid panel

HbA1c (if patient has diabetes)

Fasting glucose (FG)

Anthropometric data: weight, height – calculation of BMI (body mass index)

Demographics: age and biological sex

Medical history (structured questions):

a. Does the patient have diabetes? (If YES: record type 1 or 2; duration in years or <1 year if less than one year; medications for diabetes; presence of chronic microvascular complications: neuropathy, albuminuria, diabetic eye disease)

b. Does the patient have a history of:

Myocardial infarction (MI)

Stroke

Diagnosed peripheral arterial occlusive disease (PAD) (if YES: date of diagnosis; date of symptom progression that led to current procedure)

Previous interventions on coronary vessels (if YES: date in years, e.g., 5 years ago, or <1 year if within the past year)

Previous interventions on carotid or other head/neck vessels (if YES: date in years, e.g., 5 years ago, or <1 year if within the past year)

Additional Collected Parameters :

Previous interventions on lower limb vessels (including iliac arteries – e.g., external iliac artery): indicate the date in years, e.g., 5 years ago, or <1 year if within the past year

History of aortic aneurysm surgery (thoracic or abdominal); if YES, indicate date

History of heart failure treatment

Hypertension

Hyperlipidemia

History of cardiac arrhythmias (e.g., atrial fibrillation – AF)

Thyroid disease (hypothyroidism/hyperthyroidism only); if YES, provide most recent TSH value, if known or measured in hospital

Smoking status:

Current smoker?

If NO, date of cessation in years, <1 year if within the past year

Includes e-cigarettes (if yes, mark YES)

Chronic medications before hospital admission (excluding supplements) – chemical names

Recent interruptions in chronic medications

SGLT2 inhibitor (flozin) used before procedure: type, dose, duration, indication (diabetes, cardiology, nephrology)

7. Parameters to collect during follow-up (post-procedure):

Medications prescribed for chronic use: chemical names

Whether prescribed medications were taken regularly during follow-up

Occurrence of any of the following events**:

- a. Myocardial infarction not resulting in death
- b. Stroke (central nervous system) not resulting in death
- c. Cardiovascular death
- d. Deterioration of previously revascularized vessel (ABI decrease) confirmed by visit to vascular surgeon/angiologist
- e. Repeat intervention in previously revascularized segment due to deterioration
- f. Amputation (above or below knee) of revascularized limb
- g. Deep surgical site infection (other than skin)
- h. Major bleeding: at surgical site, gastrointestinal, other (specify location)
- i. Acute kidney injury
- j. Necrosis of the foot
- k. "Minor amputation" (foot or toes)
- l. Hospitalization due to heart failure

8. SGLT2 inhibitor (flozin) continuation during follow-up (up to 1 year):

Did the patient continue taking the flozin as before the procedure?

If not, was it discontinued immediately before surgery or during follow-up? Indicate timing.

9. Hypoglycemia in patients with diabetes:

Were there any hypoglycemic events? (Symptoms confirmed by blood glucose <70 mg/dL or asymptomatic blood glucose <70 mg/dL)

10. Type of procedure performed:

Record the specific vascular intervention.

11. ABI measurements:

Pre-procedure ABI

Post-procedure ABI

ABI if the patient underwent another procedure during follow-up due to restenosis

Notes / Guidelines:

SGLT2 inhibitors (flosins) – include also combination drugs (e.g., Xigduo). If the patient takes a combination drug, mark each component in the Excel sheet (e.g., Lonamo Duo → mark both metformin and DPP-4i; Dipeptidyl Peptidase-4 inhibitors).

If information is unavailable, enter “NZ” to confirm it was checked.

For stroke, include TIA (Transient Ischemic Attack) if confirmed.

*MALE definition, comments: Untreated loss or deterioration of patency in a previously revascularized vessel, measured by: ABI decrease (objective), Restenosis on ultrasound (objective), Shortening of claudication distance (subjective/clinical). Comment: If ABI is not performed at a center, other listed criteria may be used to confirm MALE. ABI is not strictly required if another criterion is met.

**For follow-up events (point 7):

Myocardial infarction not resulting in death, CNS stroke not resulting in death, cardiovascular death, or deterioration of previously revascularized vessel. Comment: “Deterioration requiring

visit and confirmed by physician" is sufficient; ABI measurement is optional but preferred for objective confirmation. Record method of confirmation.

For ABI (point 11): If ABI was not measured at any of the time points, mark "not performed."

The key is that inclusion criteria are met and primary, secondary, and additional endpoints are assessed.

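### The repeat-intervention component of MALE has a different trigger in Section 1 than on the follow-up form, and read literally Section 1 leaves a re-treated restenosis outside MALE

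*Protocol*

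**What the plan says.** Section 1 of the Protocol lists three MALE components, numbered here in the order given:

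- Component 1: "Untreated loss or deterioration of patency in a previously revascularized vessel (decline in ABPI").
- Component 2: "Repeat intervention in the revascularized segment due to loss of patency".
- Component 3: "Amputation (above or below the knee) of the revascularized limb".

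Section 2 makes MALE a primary outcome, and Section 3 makes its components secondary outcomes.

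Section 7 lists what is recorded during follow-up. Item d is "Deterioration of previously revascularized vessel (ABI decrease) confirmed by visit to vascular surgeon/angiologist", item e is "Repeat intervention in previously revascularized segment due to deterioration", and item f is major amputation of the treated limb.

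The Notes / Guidelines comment on the MALE definition, but only on component 1: "Untreated loss or deterioration of patency in a previously revascularized vessel, measured by: ABI decrease (objective), Restenosis on ultrasound (objective"), with claudication distance as a further measure. They say nothing about component 2.

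Section 4 has a separate secondary outcome, "Need for reintervention (readmission and procedure in the same segment"), with no reason for the procedure attached.

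**The concern.** Component 1 treats loss and deterioration as two things and accepts both, on condition that nothing was done about them. Component 2 covers the case where something was done, but names only loss. A restenosis that was treated again therefore appears to fall between the two: it is excluded from component 1 because it was treated, and from component 2 because the vessel was never lost. The form uses the word that component 2 omits.

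Two things are at stake. First, the same patient could be counted differently by someone working from Section 1 and someone working from the form. Second, under the literal Section 1 rule, treating a restenosis removes an event that would have counted had it been left alone. The study is retrospective and observational, and the clinicians decided on re-treatment. If users and non-users of SGLT2 inhibitors were re-treated at different rates, MALE could differ between them without any difference in how often vessels failed.

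**Working it through.** The protocol states no event rate, sample size or power, so there is no figure to reproduce. The check is to take each possible state of the vessel and see where the wording puts it.

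| State of the revascularised vessel | Section 1, read literally | Form, Section 7 |
|---|---|---|
| Lost, not treated | Component 1 | 7d, taking loss as the extreme of deterioration |
| Deteriorated, not treated | Component 1 | 7d |
| Lost, treated again | Component 2 | 7e, taking loss as the extreme of deterioration |
| Deteriorated but not lost, treated again | None, unless major amputation follows (component 3) | 7e, and possibly 7d, which does not require the case to be untreated |

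The first three rows agree once loss is taken as the extreme of deterioration. The fourth does not.

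The Notes do not close the gap. They keep the untreated condition on component 1, list restenosis on ultrasound as a measure of that component, and leave component 2 alone. Section 11 asks for "ABI if the patient underwent another procedure during follow-up due to restenosis". It defines no endpoint, but it shows that re-treated restenosis was foreseen.

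The dependence on re-treatment can be written down. Let *f* be the proportion of patients whose patency fails in either way, *t* the proportion of those who are re-treated, and *s* the share of failures that are complete losses (taken as the same in treated and untreated cases). Leaving amputation aside:

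- Literal Section 1, components 1 and 2: *f*(1 − *t*) + *f* *t* *s*
- With re-treated deterioration also counted: *f*(1 − *t*) + *f* *t* = *f*

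The first expression depends on *t* whenever *s* is below 1. The second does not depend on *t*.

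The values below are assumptions, not taken from the protocol: *f* = 0.20 in both groups and *s* = 0.5.

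| *t*, users v non-users | Literal count, users | Literal count, non-users | Ratio |
|---|---|---|---|
| 0.7 v 0.5 | 0.2×0.3 + 0.2×0.7×0.5 = 0.13 | 0.2×0.5 + 0.2×0.5×0.5 = 0.15 | 0.87 |
| 0.8 v 0.4 | 0.2×0.2 + 0.2×0.8×0.5 = 0.12 | 0.2×0.6 + 0.2×0.4×0.5 = 0.16 | 0.75 |
| 0.5 v 0.7 | 0.15 | 0.13 | 1.15 |
| 0.5 v 0.5 | 0.15 | 0.15 | 1.00 |

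With re-treated deterioration counted, every row is 0.20 v 0.20. The table shows only that the mechanism can act in either direction and vanishes in this setting when re-treatment is equal. It does not estimate anything for this study, and because amputation is omitted these are not MALE ratios.

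**The case against.** The strongest reply is that the form shows what was meant. Items 7a to 7c follow the three MACE components in order, and 7d to 7f follow the three MALE components in order. Item 7e is then the working version of component 2, and it covers deterioration. The protocol also sets no boundary between loss and deterioration, so loss of patency in component 2 may be shorthand for both. Two other readings would close the gap as well: that untreated qualifies only loss, or that a deterioration counts as untreated until the second procedure. A statement of which form items make up each endpoint is often left to the analysis plan, which is not at hand.

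Much of this stands. The intent was probably to count these cases. The protocol, however, adopts none of the readings that would make Section 1 say so, and the mismatch lies within its own text rather than in detail left for later.

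Three stronger conclusions are tempting, and the documents do not support them:

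- *That the MALE comparison will be biased by a stated amount or in favour of the drug.* All rates above are assumed, and nothing in the protocol indicates that re-treatment differs by SGLT2 inhibitor use.
- *That the study is set up to produce the narrow count.* Item 7e has a single trigger and no field separating occlusion from restenosis, so 7e alone cannot yield the literal Section 1 count. Someone who counts from the form will include these patients.
- *That the events are lost, or that Section 11 is a third definition of the endpoint.* The second procedure is recorded at 7e, and if it involved readmission it also meets the reintervention outcome in Section 4. Section 11 says only when an ABI is recorded.

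**Conclusion.** The point holds as an inconsistency in the definition of a primary outcome. Section 1 and item 7e give different triggers for the repeat-intervention component. On the plain wording of Section 1, a restenosis that is re-treated without the vessel being lost counts in no MALE component unless major amputation follows, while an untreated one counts. The literal rule would therefore make MALE depend on re-treatment practice.

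This rests on two readings: that untreated applies to deterioration as well as to loss, and that loss in component 2 is narrower than the loss or deterioration named in component 1. Both are the natural reading, but not the only one. The effect on the event count or on the comparison between groups cannot be given in size or direction without rates that the protocol does not contain. It is worth correcting because it decides who has a primary event and the correction is nearly free.

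**What to change.** Before outcomes are compared between groups:

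1. In Section 1, change the trigger in component 2 from loss of patency alone to loss or deterioration of patency.
2. Use the same trigger in item 7e.
3. State in the protocol that items 7d to 7f make up MALE.

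All four rows of the first table then fall in a MALE component, and the form and the definition agree.

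The cost is two wording changes and one added sentence. No new follow-up event has to be collected, because 7e already records the procedure. The downside is that MALE counts will be higher than under the literal Section 1 wording, by an amount that cannot be given in advance. A code on 7e separating occlusion from restenosis would allow the narrower count to be reported as well, but it is optional. Section 11 needs no change.

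### MALE counts patency loss only if untreated and re-treatment only in the same segment, so a failed vessel re-treated elsewhere fits no component, while follow-up item d would record it

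*Protocol*

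**What the plan says.** Section 2 gives "Primary Outcome Measures: MALE and MACE". Section 1 defines MALE by three components:

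1. "Untreated loss or deterioration of patency in a previously revascularized vessel (decline in ABPI")
2. "Repeat intervention in the revascularized segment due to loss of patency"
3. "Amputation (above or below the knee) of the revascularized limb"

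The MALE note under Notes / Guidelines keeps both the untreated condition and the vessel as unit: "MALE definition, comments: Untreated loss or deterioration of patency in a previously revascularized vessel, measured by: ABI decrease (objective"). It goes on to accept ultrasound restenosis or a shorter claudication distance as alternatives to ABI.

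The follow-up form in Section 7 collects the first two components as item d, "Deterioration of previously revascularized vessel (ABI decrease) confirmed by visit to vascular surgeon/angiologist", and item e, "Repeat intervention in previously revascularized segment due to deterioration". Item d does not carry the untreated condition. Item e keeps the segment limit, as does the Section 4 outcome "Need for reintervention (readmission and procedure in the same segment").

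The protocol defines neither segment nor the time at which a loss of patency is judged to be untreated.

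**The concern.** Components 1 and 2 look meant to divide patency failures between them: those left alone and those re-treated. They do not cover all failures, because component 1 excludes any treated failure while component 2 takes back only those treated in one segment. A failure re-treated elsewhere falls between the two.

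Whether a given failure is a primary event then depends on what was done about it and where. In a retrospective observational study, later re-treatment is a non-randomized care decision. An outcome that depends on it can lose real failures and, if care differs between the groups, can carry that difference into the drug comparison. The individual components, which are secondary outcomes in Section 3, inherit the same rule.

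In addition, an abstractor who follows item 7d and one who follows Section 1 could score the same patient differently.

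**Working it through.** The protocol states no event rate, sample size or power, so there is no figure to reproduce. The check is to apply the definitions to each course that a failed index vessel can take without major amputation (component 3 not met).

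| Course after patency loss | Component 1 | Component 2 | MALE by Section 1 | Follow-up form |
|---|---|---|---|---|
| Left alone | met | not met | yes | 7d, if confirmed at a specialist visit |
| Re-treated in the segment | not met (treated) | met | yes | 7e, and possibly 7d |
| Re-treated outside the segment | not met (treated) | not met (other segment) | **no** | 7d, if confirmed at a specialist visit |

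The third row is the gap. It needs two features together: the untreated condition in component 1 and the narrower unit in component 2. Remove the untreated condition and the third row meets component 1.

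Other text does not close the gap in the primary definition:

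- The MALE note repeats the untreated condition and only adds ways of measuring the loss.
- Item 7e and the Section 4 reintervention outcome repeat the segment limit.
- Section 11 asks for an ABI if there was another procedure for restenosis, without a segment limit, but it does not ask for side or segment and is not part of the outcome definition.
- Item 7d would capture the case, but it contradicts Section 1 rather than amending it.

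**Illustration only; every rate is an assumption.** Let 15% of each group have MALE by other routes. Let a share p have a failure whose re-treatment, if done, lies outside the segment, and let r be the proportion of these that is re-treated. Suppose none of those re-treated is scored through 7d. Then

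MALE scored by Section 1 = 0.15 + p(1 − r).

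The true proportion is 0.15 + p in both groups, so the true risk ratio (users to non-users) is 1.

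| p | r = 0.60 users, 0.40 non-users | Risk ratio | Split reversed | Risk ratio | r = 0.50 in both: missed per group (p × r) |
|---|---|---|---|---|---|
| 0.05 | 17% vs 18% | 0.94 | 18% vs 17% | 1.06 | 2.5 points |
| 0.10 | 19% vs 21% | 0.90 | 21% vs 19% | 1.11 | 5.0 points |
| 0.15 | 21% vs 24% | 0.88 | 24% vs 21% | 1.14 | 7.5 points |

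For example, with p = 0.10: 0.15 + 0.10 × 0.40 = 0.19, 0.15 + 0.10 × 0.60 = 0.21, and 0.19 / 0.21 = 0.905. With equal re-treatment the ratio stays at 1 and only events are lost. The direction of any bias is set entirely by the assumed split.

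**The case against.** Several points on the other side are sound.

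- **The data may be captured.** Item 7d has no untreated condition, and the note on follow-up events accepts deterioration confirmed by a physician. A failure confirmed at a visit before re-treatment might also count under Section 1, since the time of judgement is not fixed. This stands, and it narrows the point to a conflict between form and definition. It does not remove it, because the MALE note repeats the untreated condition.
- **Segment can be read broadly.** A bypass of a failed treated segment can reasonably be taken as repeat intervention in that segment. This also stands: on a broad reading the gap is rarer, and only procedures beyond the segment so understood are lost.
- **Same-segment reintervention may be deliberate.** It appears in component 2, item 7e and Section 4, and a patency endpoint may properly leave out native disease progression. That explains a segment limit on its own. It does not explain why a failure of the index vessel counts when left alone and stops counting when treated elsewhere.

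A reader might infer three stronger claims, which the protocol does not support.

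- *The fault is that MALE uses three anatomical units: vessel, segment and limb.* Amputation is limb-level by nature and shows no inconsistency. Nor is it a general defect that ABI cannot localize failure, since the note accepts ultrasound, which can.
- *The MALE rate is understated and the drug will look protective.* The protocol gives neither the frequency of such cases nor any sign that re-treatment differs by group, and reversing the assumed split reverses the bias.
- *The whole endpoint must move to limb level.* That would bring in native progression elsewhere in the limb and is not needed to close the gap.

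**Conclusion.** The gap in the definition holds on the literal wording of Section 1 and the MALE note, and so does the conflict with item 7d. It is more than missing detail, because the protocol states a primary-outcome rule under which the same failure counts or not according to later management.

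Its effect on the results cannot be sized from the protocol. The illustrative risk ratios of 0.88 to 1.14 rest wholly on assumed rates and on no rescue through item 7d. They show that the mechanism can work in either direction, not that it does. A bias in the comparison requires re-treatment patterns to differ between users and non-users. With equal patterns and the equal true risks assumed above, the cost is missed events only. The sponsor should correct the wording.

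**What to change.** 1. Delete the untreated condition from component 1 in Section 1 and from the MALE note so that both agree with item 7d. Confirmed loss or deterioration of patency in the index revascularized vessel then counts whether or not it is treated later.
2. Use that same vessel as the unit in component 2 and item 7e. State that a bypass or other procedure done because the vessel or its repair failed counts, wherever that procedure is placed.
3. Define segment, and record side and segment for the index procedure and for each later one.
4. Report MALE with same-segment reintervention only as a sensitivity analysis.

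The cost is a few lines of text and some extra abstraction: Section 10 asks for the specific intervention but does not name side or segment. Some progression in the index vessel beyond the treated segment will be counted, which the sensitivity analysis separates. Components 1 and 2 will also overlap. This is harmless for the composite if each patient counts once, but the Section 3 reporting of individual components should say so. Nothing here touches how patients are treated.

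### Entry depends on at least 30 days of follow-up, so early deaths may be screened out, and the follow-up data list has no event date, last contact or non-cardiovascular death

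*Protocol*

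**What the plan says.** The protocol describes a retrospective observational study. Section 1 sets the observation period: "Follow-up period: ONE YEAR: assessment at 30 days, 3 months, and 12 months post-procedure". It covers open and minimally invasive procedures "performed electively or urgently", and Section 5 admits "Surgical procedure on peripheral vessels due to acute or chronic ischemia". Cardiovascular death is one of the three MACE components, and MACE and MALE are the primary outcomes (Sections 1 and 2).

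The third inclusion criterion in Section 5 is "Ability to follow up the patient for at least 30 days up to 1 year after the vascular procedure".

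Section 7 sets out the post-procedure data. For outcomes it asks for "Occurrence of any of the following events", followed by items a to l. Cardiovascular death is the only death on that list. Sections 8 to 11 cover flozin continuation, hypoglycemia, procedure type and ABI values. The Notes ask how a deterioration was confirmed, but not when. For missing items they say: "If information is unavailable, enter “NZ” to confirm it was checked".

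Elsewhere the protocol does ask for timing. Section 6 wants, for peripheral arterial disease, "date of diagnosis; date of symptom progression that led to current procedure". Section 8 asks about a stopped flozin: "If not, was it discontinued immediately before surgery or during follow-up? Indicate timing".

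**The concern.** There are two linked problems.

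**Selection on the future.** In a retrospective study, whoever builds the cohort already knows how long each patient could be followed. A criterion of at least 30 days of follow-up therefore makes entry depend on what happened after the procedure. If it is applied literally, a cardiovascular death on day 10 removes the patient from the cohort instead of counting as a primary event. Urgent procedures and acute ischemia are included, so such deaths are plausible. Two abstractors who read the criterion differently would build different cohorts from the same records.

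**Unequal follow-up that cannot be corrected.** The criterion accepts anything from 30 days to a year, while the outcome period is one year. If status is recorded once per patient, without dates, the listed items leave two simple analyses. One counts patients with short follow-up as event-free, which understates 12-month risk. The other drops those with unknown status but keeps observed events, which overstates it. The code NZ shows that status is unknown. It does not show when the patient was last known to be event-free, or whether the patient died of another cause.

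Absolute risks are affected in either case. The drug comparison is distorted if early death or follow-up length differs between exposed and unexposed patients; the protocol gives no basis for computing by how much.

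**Working it through.** The protocol states no event rate, sample size or effect size, so there is no figure of its own to reproduce. All numerical inputs below are assumptions chosen to show direction and order of size.

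**1. Reading the text.** Under one reading of Section 5, outcome status must be known, and a known death satisfies that. Under the other, the patient must be observable for 30 days, and a death on day 10 fails. No section says that early deaths are kept. The closing sentence of the Notes stresses both that inclusion criteria are met and that endpoints are assessed, so it does not decide between the readings.

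**2. Early cardiovascular deaths removed.** Let R be the true 12-month MACE risk and d the proportion dying of cardiovascular causes before day 30. Removing them from numerator and denominator gives (R − d)/(1 − d). With R = 0.12:

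| d | Observed risk |
|---|---|
| 0.005 | 0.115/0.995 = 0.1156 |
| 0.01 | 0.110/0.990 = 0.1111 |
| 0.02 | 0.100/0.980 = 0.1020 |
| 0.03 | 0.090/0.970 = 0.0928 |

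For the comparison, take 12% in unexposed and 10.5% in exposed patients, a true risk ratio of 0.875:

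| d, unexposed vs exposed | Observed risk ratio |
|---|---|
| 2% vs 1.75% (proportional to risk) | 0.0891/0.1020 = 0.873 |
| 2% vs 2% | 0.0867/0.1020 = 0.850 |
| 2% vs 1% | 0.0960/0.1020 = 0.940 |

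For cardiovascular death alone the loss can be larger. With an assumed 4% dying before day 30 and 6% of the remainder dying later, the true risk is 0.04 + 0.96 × 0.06 = 0.0976, and 0.04/0.0976 = 41% of these deaths disappear. With 2% early, the true risk is 0.02 + 0.98 × 0.06 = 0.0788, and the share lost is 0.02/0.0788 = 25%.

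**3. Short follow-up.** Assume a true 12-month risk of 20%. A share s of patients has follow-up uniform on 30 to 365 days, and the rest are complete. Let m be the mean risk observed in the short patients. Two event patterns were used:

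- Constant hazard (9% of events by day 30): the yearly hazard is −ln(0.8) = 0.2231 and survival at day 30 is 0.9818, so m = 1 − (0.9818 − 0.8)/(0.2231 × 335/365) = 0.112.
- A quarter of events by day 30, constant hazard afterwards: survival is 0.95 at day 30 and 0.80 at one year, so m = 1 − (0.95 − 0.80)/ln(0.95/0.80) = 0.127.

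Counting short patients without an event as event-free gives ev = (1 − s) × 0.2 + s × m. Omitting the unknowns gives ev/(ev + (1 − s) × 0.8).

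| s | Counted event-free | Unknowns omitted |
|---|---|---|
| 0.10 | 0.191 to 0.193 | 0.210 to 0.211 |
| 0.25 | 0.178 to 0.182 | 0.229 to 0.233 |

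With no drug effect, equal shares in both groups give a risk ratio of 1.00. With 10% short in unexposed and 25% in exposed patients, the ratio is 0.931 to 0.943 (counted event-free) or 1.090 to 1.101 (unknowns omitted).

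**The case against.** The criterion speaks of the ability to follow a patient up, not of survival to day 30. Several features favour keeping early deaths: a 30-day assessment is planned, cardiovascular death is a primary component and is listed in Section 7 with no minimum time, and no exclusion criterion mentions early death. This has force. It shows that the benign reading may be the intended one, so exclusion is a possibility and not a demonstrated fact. It does not remove the ambiguity, because nothing instructs the abstractor to keep these patients.

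The three planned assessments may imply that events are recorded at each one, which would give coarse interval timing. Section 7 does not say so, and this would still leave out last contact and non-cardiovascular death. The Notes mention an Excel sheet that is not shown and may hold more columns. That is possible, but Section 7 is the only stated specification of the outcome data.

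Censoring and competing risks are normally matters for an analysis plan, and one may exist. It can choose the method. It cannot change who was eligible or supply dates and deaths that were never extracted.

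Variable follow-up is ordinary in retrospective cohorts and does not by itself contradict a one-year maximum. That is accepted; the difficulty is variable follow-up without the dates needed to handle it. It is also fair that the magnitudes are all assumed, and that the drug comparison hardly moves when early deaths are proportional to risk or short shares are equal.

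**Conclusion.** The concern holds and should be fixed. As written, the criterion can produce a cohort without the patients who die before day 30, and the listed follow-up items do not allow unequal observation or competing death to be handled properly.

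The size cannot be derived from the protocol. The absolute-risk illustrations range from negligible (12% becoming 11.6%) to material (12% becoming 9.3%, or 20% becoming about 18% or 23%). For the drug comparison, the risk ratio stays essentially unchanged if early death is proportional to risk or short follow-up is equally common in both groups. In the differential scenarios it shifts by roughly 3% to 10%, in either direction. The early-death results depend on the literal reading of Section 5. The short-follow-up results depend on status being recorded once without dates, and on the assumed shares and event patterns.

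**What to change.** Reword the Section 5 criterion so that eligibility is determined at the procedure date, and state that patients who die before day 30 are retained and their events counted. Naming early non-fatal events as well does no harm, although patients who have one and survive to day 30 are not excluded under either reading.

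Add to Section 7 the date of first occurrence of each event, the date of last contact, and the date and cause of any death. The analysis can then censor at last contact, treat non-cardiovascular death as a competing event, and report risks at 30 days, 3 months and 12 months.

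The cost is one reworded criterion and a few date columns taken from the same records, so slightly more extraction. Some patients will enter with short, censored follow-up. The change is cheapest before extraction is finished, since afterwards charts would have to be reopened.
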